### **2.8.3 Definition of Efficacy Endpoints**

Efficacy will be defined at different timepoints during the trial. Specific endpoints are:

- a) SVR4 (Sustained Virologic Response 4 weeks after the end of all study therapy). The subject has HCV RNA <LLOQ [either TD(u) or TND] 4 weeks after the end of all study therapy
- b) SVR12 (Sustained Virologic Response 12 weeks after the end of all study therapy): The subject has HCV RNA <LLOQ [either TD(u) or TND] 12 weeks after the end of all study therapy.
- c) SVR24 (Sustained Virologic Response 24 weeks after the end of all study therapy). The subject has HCV RNA <LLOQ [either TD(u) or TND] 24 weeks after the end of all study therapy.

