### **2.8.4 Definition of Virologic Failure: Futility, Virologic Breakthrough, Rebound, and Relapse**

Lack of efficacy at different timepoints in the trial will be categorized as:

- Futility:

Subject has HCV RNA LLOQ [TD(q)] at treatment Week 4 with confirmation. The results of the next available blood draw will be used as the confirmatory test. This confirmatory test must be obtained within 2 weeks. Futility is defined as HCV RNA  $\geq 25$  IU/mL from the confirmatory test.

- Rebound

Subject has a rebound defined as  $>1$  log10 increase in HCV RNA from nadir while on treatment and confirmed from a separate blood draw within 2 weeks.

- Virologic breakthrough:

Subject has a confirmed HCV RNA  $\geq$  LLOQ [TD(q)] after being  $< 25$  IU/mL previously [TD(u) or TND]. Confirmation is defined as an HCV RNA  $\geq$  LLoQ from a separate blood draw repeated within 2 weeks.

- Relapse:

Subject has a confirmed HCV RNA  $\geq$  LLoQ [TD(q)] following end of all study therapy, after becoming undetectable (TND) at end of treatment. Confirmation is defined as an HCV RNA  $\geq$  LLoQ from a separate blood draw repeated within 2 weeks.

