-  If HCV RNA is collected during viral failure confirmation visit and the subject is confirmed viral failure during therapy (i.e. breakthrough/rebound), then the sample collection for HCV RNA is not needed for the early discontinuation visit

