### **10.4 Analyses for the secondary objectives**

Most of secondary analyses will be exploratory and will be performed as described previously (i) to evaluate the safety and tolerability of EBR/GZR treatment, (ii) to determine the proportion of subjects who attain SVR at 4 and 24 weeks after cessation of treatment (SVR4 and SVR24), (iii) to evaluate the proportion of subjects with virological failure and (iv) to evaluate the emergence of viral resistance to EBR/GZR during treatment and after cessation of treatment. Finally, to evaluate the kinetics of circulating HCV RNA during treatment and after cessation of treatment, a descriptive statistical analysis will be proposed. This analysis will be completed using random-effects models useful to evaluate kinetics taking into account between and within patient variability.

To better understand the potential for Resistance Associated Variants (RAVs) with EBR and/or GZR, samples will be retained from Day 1 and viral failure visits and RAVs will be assessed for any subject who has detectable virus above 1000 UI/mL and has met a virologic failure criteria. Subjects who discontinue the treatment will continue to participate in the scheduled follow-up activities including monitoring for resistance.

Exploratory IL28B genotyping may also be conducted to detect genetic variations associated with response to treatment of hepatitis C. A separate signature will be required to document a subject's agreement to provide additional samples for optional genetic research.

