**Table 2. Virologic Failure**

	GZR + EBR + RBV 8 weeks (n = 30)	GZR + EBR 8 weeks (n = 31)
Virologic failure		
Breakthrough/rebound	0	0
Relapse	2	2
At FUW4	1	1
At FUW12	1	1

EBR = elbasvir; FUW = follow-up week; GZR = grazoprevir; RBV = ribavirin.

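### Relapse is defined only for patients with undetectable HCV RNA at end of treatment, so a patient detected below LLOQ at week 8 who recurs is either labelled breakthrough or left unclassified

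*Combined protocol and SAP*

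**What the plan says.** **Response (Section 2.8.3).** SVR12 is met when "The subject has HCV RNA <LLOQ [either TD(u) or TND] 12 weeks after the end of all study therapy". SVR4 and SVR24 follow the same rule, so both states below LLOQ count as success.

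**Failure categories (Section 2.8.4).**
- Relapse is confirmed HCV RNA at or above LLOQ "following end of all study therapy, after becoming undetectable (TND) at end of treatment".
- Futility is assessed "at treatment Week 4 with confirmation".
- Rebound is a rise from nadir "while on treatment and confirmed from a separate blood draw within 2 weeks".
- Breakthrough is confirmed HCV RNA at or above LLOQ after a value under 25 "IU/mL previously [TD(u) or TND". Both states below LLOQ are named, and the sentence does not say when the recurrence must occur.

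**Flow chart, footnote 6 (Section 7).** The footnote describes the case where "the subject is confirmed viral failure during therapy (i.e. breakthrough/rebound", which places breakthrough and rebound within the treatment period.

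**Resistance testing (Section 10.4).** "RAVs will be assessed for any subject who has detectable virus above 1000 UI/mL and has met a virologic failure criteria". Samples are kept from Day 1 and from viral failure visits.

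The proportion with virologic failure and the emergence of resistance are both secondary objectives (Section 3.2).

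**The concern.** Response and relapse start from different end-of-treatment states. A patient who is TD(u) at week 8 is on course for SVR by Section 2.8.3, yet Section 2.8.4 does not allow that patient to relapse.

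This matters because relapse is the failure mode that bears most directly on a shortened regimen. In the 8-week genotype 1b study in Annexe 1, all four virologic failures were relapses (two per arm), and the "Breakthrough/rebound" row is zero in both arms. A post-treatment recurrence that is misnamed or uncounted distorts the result that a reader of an 8-week trial will look for.

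Resistance data are also at stake. Testing depends on meeting a failure criterion, and post-baseline samples are kept only from failure visits. If the visit is not classed as a failure, the plan gives no ground for keeping that sample, so a later reclassification might not recover it.

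**Working it through.** The plan states no figure on this point, so there is none to reproduce. The check applies each definition to one patient: TD(u) at week 8, then HCV RNA at or above LLOQ after treatment, confirmed on a second draw within 2 weeks.

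| Category | Deciding condition | Met? |
|---|---|---|
| Futility | treatment Week 4 | No |
| Rebound | while on treatment | No |
| Relapse | TND at end of treatment | No |
| Breakthrough, literal text of 2.8.4 | earlier value <25 IU/mL, TD(u) or TND; no time limit | Yes |
| Breakthrough, limited to therapy as in footnote 6 | failure must occur on treatment | No |

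The LLOQs in Section 2.8.2 are 15 and 12 IU/mL, so a TD(u) result on either assay is below 25 IU/mL and meets the breakthrough precondition.

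**Consequences of each reading**
- Literal: the patient counts in the overall virologic-failure proportion and can be tested for resistance above 1000 IU/mL, but a post-treatment recurrence is reported as breakthrough. On this reading every patient who was TND at end of treatment and then relapses also meets breakthrough, so the two categories overlap.
- On-therapy only: no criterion is met. The patient is missing from the virologic-failure proportion, and the testing and retention rules in Section 10.4 are not triggered.

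**Scale (illustrative)**

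Inputs: n = 120 and assumed SVR12 of 96% (Section 10.1); 2 relapses in 31 patients on the 8-week regimen without ribavirin (Section 2.7). The share of failures who are TD(u) at week 8, q, is not given; 5% to 30% is an assumption.

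- Expected SVR12 failures at the planning rate: 120 × (1 − 0.96) = 4.8.
- Expected at the earlier relapse rate: 120 × 2/31 = 7.74.
- Affected patients = expected failures × q:
  - planning rate: 4.8 × 0.05 = 0.24 to 4.8 × 0.30 = 1.44
  - earlier rate: 7.74 × 0.05 = 0.39 to 7.74 × 0.30 = 2.32
- Chance of at least one affected patient, treating failures as independent, is 1 − (1 − q)^k:
  - k = 5: 1 − 0.95^5 = 0.23 to 1 − 0.70^5 = 0.83
  - k = 8: 1 − 0.95^8 = 0.34 to 1 − 0.70^8 = 0.94
- Weight of one patient: 1/120 = 0.83 percentage points of the virologic-failure proportion, or 1/4.8 = 21% of the expected failures.

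**The case against.** A reader might infer that the patient fits no failure category at all and can never be sequenced. The documents do not establish that. The breakthrough sentence names TD(u) and has no on-treatment limit, so on its words the patient is a virologic failure and is eligible for resistance testing. The total would then be right and only the label odd. Footnote 6 points the other way, but its purpose is to say when a repeat sample is unnecessary at early discontinuation; it is not a definition. This part of the objection stands, and the complete gap is conditional.

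The on-therapy reading is still the more coherent one. Without a time limit, breakthrough absorbs every relapse that Section 2.8.4 defines separately, and Annexe 1 also reports breakthrough/rebound apart from relapse. Neither reading gives a correct classification.

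The objections on size also stand in part:
- No TD(u) frequency is given. Section 2.8.2 gives each assay the same value for detection and quantitation, so the group may be small.
- Section 10.2 counts most missing results as failures, so the 4.8 includes non-virologic failures and the base for relapse may be lower. For the same reason SVR12 failures and virologic failures need not match in any case.
- The failure table in Annexe 1 does not give end-of-treatment TD(u) or TND status, so it does not show that this rule would have missed any of the four relapses.

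Section 10.3 also requires a description of patients without SVR12, so such a patient would stay visible in the report. That does not restore the category count or the resistance sample.

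**Conclusion.** The relapse definition is inconsistent with the SVR definitions, and the text does not assign a TD(u) week-8 patient who recurs to one proper category. The literal reading mislabels the recurrence as breakthrough. The on-therapy reading leaves it out of the virologic-failure proportion and outside resistance testing.

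The primary endpoint does not change: a patient at or above LLOQ at post-treatment week 12 fails SVR12 under any label. A reader might infer a threat to the main efficacy result, and the documents give no support for that.

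The likely size is from none to about two patients, on an assumed 5% to 30% TD(u) share and either the planning failure rate or the 2/31 relapse rate. That is few patients, but the virologic-failure and resistance results will rest on few events. Severity is moderate and confined to secondary objectives, most of whose analyses Section 10.4 calls exploratory.

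**What to change.** 1. In Section 2.8.4, define relapse as confirmed HCV RNA ≥LLOQ after the end of therapy in a subject with HCV RNA <LLOQ, TD(u) or TND, at end of treatment. This matches Section 2.8.3.
2. Reconcile the breakthrough definition in Section 2.8.4 with flow-chart footnote 6 by stating whether breakthrough is on-treatment only, so that each failure falls in exactly one category. Changing the relapse wording alone would leave TD(u) and TND relapsers literally meeting both definitions.
3. In Section 10.4, apply resistance testing and sample retention to the reconciled categories, keeping the 1000 IU/mL limit.

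The cost is a line or two of text and at most one or two more sequenced samples. The relapse change affects only how post-treatment results are classified.

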### **2.8.5 Safety Endpoints**

The safety and tolerability of EBR/GZR combination will be assessed by a clinical evaluation of adverse experiences and other study parameters including vital signs, physical examinations, and standard laboratory safety tests at appropriate time points as specified in the Study Flow Chart (Table 7). Adverse experiences are graded and recorded according to Section 8.2.4/Table 9. Subjects may be asked to return for unscheduled visits in order to perform additional safety monitoring.

## **3. OBJECTIVES**

### **3.1 Primary objective**

The primary objectives of this study are as follows:

- To evaluate the efficacy of of Elbasvir/Grazoprevir Fixed-Dose Combination for 8 Weeks in Treatment-Naïve, HCV GT1b-Infected Patients, with non- severe fibrosis as measured by the proportion of subjects with sustained viral response 12 weeks after cessation of treatment (SVR 12).
- To evaluate the safety and tolerability of EBV/GZR treatment

### **3.2 Secondary objective**

The secondary objectives of this study are as follows:

- To determine the proportion of subjects who attain SVR at 4 and 24 weeks after cessation of treatment (SVR4 and SVR24)
- To evaluate the proportion of subjects with virologic failure
- To evaluate the kinetics of circulating HCV RNA during treatment and after cessation of treatment.
- To evaluate the emergence of viral resistance to EBR/GZR during treatment and after cessation of treatment

## 4. STUDY DESIGN

### 4.1 Trial Design

This is a multi-site, open-label evaluating the efficacy of GRAZOPREVIR (100 mg - second-generation protease inhibitor) in combination with ELBASVIR (50 mg - NS54A inhibitor), in treating non-cirrhotic, treatment-naïve (TN) subjects with chronic hepatitis C (CHC) infection with genotypes 1b to be conducted in conformance with Good Clinical Practice.

Approximately 120 subjects will be enrolled in this study.

There will be one treatment group with EBR/GZR (50/100 mg) once daily without regards to food for 8 weeks.

Several measures have been included in order to limit risk to the study subject.

- Subjects will be discontinued from all study therapy (where applicable) if they meet any of the criteria for discontinuation (details in Section 5.4).
- Study therapy will also be discontinued for subjects who meet criteria for virologic failure (defined in section 2.8.4).
- In the event there is an unacceptable rate of virologic failure (details in section 2.8.4) or discontinuation of study medications due to safety concerns, the treatment or the entire study may be terminated.

Specific procedures to be performed during the trial, as well as their prescribed times and associated visit windows, are outlined in the Trial Flow Chart - Table 7 Details of each procedure are provided in Section 8.1 – Trial Procedures.

## 4.2 Study category

This is a Clinical trial of investigational medicinal products.

## 5. STUDY POPULATION

### 5.1. Subject Inclusion Criteria

Subjects must meet all of the following inclusion criteria to be eligible for participation in this study:

- 1 - Willing and able to provide written informed consent
- 2 - Male or female, age  $\geq 18$  years
- 3 - Body Mass Index (BMI)  $\geq 18$  kg/m^2
- 4 - HCV RNA  $\geq 10^4$  IU/mL at Screening
- 5- Chronic HCV infection ( $\geq 6$  months) documented by prior medical history or liver biopsy, only genotype 1b virus. (Positive for anti HCV antibody, HCV RNA, or an HCV genotype)
- 6 - Treatment-naïve with no prior exposure to any IFN, RBV, or approved or experimental HCV-specific DAA
- 7- Non severe fibrosis (F < 2) according to combination of this two tests :
  - **Fibroscan® lower than 9.5 kPa AND Fibrotest lower than 0.59**
- 8 - Females of childbearing potential (as defined in protocol Appendix 4) must have a negative serum pregnancy test at screening and a negative urine pregnancy test on Day 1 prior to enrollment
- 9 - Male subjects and female subjects of childbearing potential who engage in heterosexual intercourse must agree to use 2 effective method(s) of contraception from at least two weeks prior to Day 1 through 14 days after the last dose of study drugs.  
If acceptable by local regulatory agencies, methods of birth control allowed in the study are: intrauterine device (IUD), diaphragm with spermicide, hormonal contraceptives (e.g., birth control pills, transdermal patch, or injectables), contraceptive sponge, female condom, male condom with spermicide or vasectomy.  
Note: Periodic abstinence (e.g., abstinence only on certain calendar days, abstinence only during ovulation period, use of symptothermal methods, use of post-ovulation methods and withdrawal) are not acceptable methods of contraception.

10 - A female subject who is not of reproductive potential is eligible without requiring the use of contraception. A female subjects who is not of reproductive potentials is defined as one who has either 1) reached natural menopause (defined as 12 months with no menses without an alternative medical cause), 2) 6 weeks post surgical bilateral oophorectomy with or without hysterectomy, or 3) bilateral tubal ligation.

11 - A male subject who is not of reproductive potential is eligible without requiring the use of contraception. A male subject who is not of reproductive potential is defined as: one who has undergone a successful vasectomy. A successful vasectomy is defined as: (1) microscopic documentation of azoospermia, or (2) a vasectomy more than 2 years ago with no resultant pregnancy despite sexual activity post vasectomy.

12 - Lactating females must agree to discontinue nursing before starting study drug

13 - Subject must be of generally good health, with the exception of chronic HCV infection, as determined by the Investigator

14 - Subject must be able to comply with the dosing instructions for study drug administration and able to complete the study schedule of assessments

## 5.2 Subject Exclusion Criteria

Subjects who meet **any** of the following exclusion criteria are **not** to be enrolled in this study.

1 - Is under the age of legal consent, is mentally or legally incapacitated, has significant emotional problems at the time of pre-study screening visit or expected during the conduct of the study or has a history of a clinically significant psychiatric disorder which, in the opinion of the investigator, would interfere with the study procedures.

2 - Current or prior history of any of the following:

a) Clinically significant illness (other than HCV) or any other major medical disorder that may interfere with subject treatment, assessment or compliance with the protocol; subjects currently under evaluation for a potentially clinically significant illness (other than HCV) are also excluded

b) Gastrointestinal disorder or post-operative condition that could interfere with the absorption of the study drug

c) Difficulty with blood collection and/or poor venous access for the purposes of phlebotomy

d) History of decompensation (e.g., clinical ascites, encephalopathy, and/or variceal hemorrhage)

e) Solid organ transplantation (including hematopoietic stem cell transplants) other than cornea and hair.

f) Significant cardiac disease

g) Unstable psychiatric condition including hospitalization, suicidal attempt, and/or a period of disability as a result of their psychiatric illness within 2 years prior to Screening

h) Malignancy within the 5 years prior to Screening, with the exception of specific cancers that have been cured by surgical resection (e.g., basal cell skin cancer, etc.). Subjects under evaluation for possible malignancy are not eligible

l) Significant drug allergy (e.g., hepatotoxicity)

3 - Subject has the following laboratory parameters at Screening:

a) ALT > 10 x the upper limit of normal (ULN)

b) AST > 10 x ULN

c) Direct bilirubin > 1.5 x ULN

d) Platelets < 75,000/ $\mu$ L

e) HbA1c > 8.5%

f) Creatinine clearance < 50 mL/min as calculated by the Cockcroft-Gault equation

g) Hemoglobin < 10 g/dL

h) Albumin < 3 g/dL

i) INR > 1.5 x ULN unless subject has known hemophilia or is stable on an anticoagulant regime affecting INR

4 - Chronic liver disease of a non-HCV etiology (e.g., hemochromatosis, Wilson's disease, alfa-1 antitrypsin deficiency, cholangitis)

5 - Infection with hepatitis B virus (HBV) or human immunodeficiency virus (HIV)

6 - Clinically-relevant alcohol or drug abuse within 12 months of Screening.

- a. Alcohol, intravenous drugs, inhalational (not including marijuana), psychotropic, narcotics, cocaine use, prescription or over-the-counter drugs: within 1 year of the screening visit, or if shorter, is judged by investigator to be capable of complying with study procedures
- b. receiving opiate agonist substitution therapy within 1 year of screening visit, or if shorter, is judged by investigator to be capable of complying with study procedures
- c. history of marijuana use if deemed excessive by a physician investigator or interferes with the subject's daily function. If subject's marijuana use is not deemed excessive and does not interfere with daily function, subject must agree to discontinue any current use of recreational marijuana prior to entry into trial and throughout the trial period  
A positive drug screen will exclude subjects unless it can be explained by a prescribed medication; the diagnosis and prescription must be approved by the investigator

7 - Use of any prohibited concomitant medication listed in Section 9.8 of this protocol within 2 weeks prior to day 1.

8 - Known hypersensitivity to the study drug, the metabolites, or formulation excipient

9 - Is currently participating or has participated in a study with an investigational compound within 30 days of signing informed consent and is not willing to refrain from participating in another study. Collection of additional blood, urine, or tissue samples or additional data,

beyond that specified in this protocol, is prohibited (other than that related to subject's medical care).

10 - (female) is pregnant, lactating, expecting to conceive or donate eggs, or is of childbearing potential and unwilling to commit to two methods of birth control throughout treatment and after the completion of all treatment (see Inclusion Criteria); or male subject is planning to impregnate or provide sperm donation or has a female sexual partner of childbearing potential and is unwilling to commit to using a two methods of birth control throughout treatment and after the completion of all treatment (see Inclusion Criteria).

11 - Had a life-threatening SAE during the screening period.

12 - Is a member or a family member of the investigational study staff or sponsor staff directly involved with this study.

13 - Has evidence or history of chronic hepatitis not caused by HCV, including but not limited to nonalcoholic steatohepatitis (NASH), drug-induced hepatitis, and autoimmune hepatitis.

**NOTE:** Subjects with history of acute non-HCV-related hepatitis, which resolved > 6 months before study entry, may be enrolled.

14 - For subjects diagnosed with diabetes mellitus, documented HbA1c >8.5% (to exclude uncontrolled diabetes).

15 - Has any of the following conditions:.

- Subject with a history of gastric surgery (e.g., stapling, bypass) or subject with a history of malabsorption disorders (e.g., celiac sprue disease).
- Any medical condition requiring, or likely to require, chronic systemic administration of corticosteroids during the course of the trial.

16 - Has exclusionary laboratory values as listed below (see Table 5 for unit conversions of some laboratory values specified below):

**Note:** If any of the laboratory exclusion criteria below are met, the site may have the abnormal value retested one time.

**Table 5 : Exclusionary laboratory values**

Laboratory Assessment	
hemoglobin	< LLN (lower limit of normal) of laboratory reference range
neutrophils	<1.5 x 10  /μL (<1.2 x 10  /μL for Blacks)
platelets	<75 x 10  /μL
direct bilirubin	>1.5 x ULN
Total Bilirubin	>1.6 mg/dL unless history of Gilbert's disease. (If Gilbert's disease is the proposed etiology, this must be documented in the subject's chart)

Serum Albumin	< 3.0 g/dL (lower limit of normal) of laboratory reference range
creatinine clearance	<50 mL/min
INR	>1.5
ALT	>350
AST	>350

